## **STUDY SUMMARY**

Title: Cochlear Promontory Stimulation for Treatment of Tinnitus: Towards Developing an Implantable Device

IRB Protocol Number: 17-004832

Methodology: Prospective, investigational

Target subject accrual: 100

Expected duration of study: 10 years

Subject participation duration: 4 days [3 sequential clinic visits scheduled 7 days (+14/- 2 days) apart with a 3 month follow up visit]

Primary Objective: Use of a cochlear promontory stimulation electrode to provide safe, short term relief of tinnitus.

Secondary Objective: Map the optimum regions of the cochlear promontory in planning for an implantable electrical device for long term tinnitus suppression.

Principal Investigator: [name]

## 1 BACKGROUND

Tinnitus is the perception of sound when no external noise is present. The exact mechanism(s) underlying the development and maintenance of tinnitus remains largely unknown. The Center for Disease Control (CDC) estimates over 50 million — nearly 15% of the general public — experience some form of tinnitus [9]. Roughly 20 million people struggle with burdensome chronic tinnitus, with 2 million experiencing extreme and debilitating symptoms [9].

Currently, there are no Food and Drug Administration (FDA) approved pharmacological therapies or surgical devices available for the treatment of tinnitus. The 2014 Clinical Practice Guideline on tinnitus from the American Academy of Otolaryngology – Head and Neck Surgery summarized the existing state of tinnitus management by stating “A cure for primary tinnitus does not yet exist, and despite claims to the contrary, no method has been proven to provide long-term suppression of tinnitus.” Existing treatment methods largely focus on counseling, cognitive behavioral therapy, masking, and sound therapy for habituation – strategies that may render tinnitus more tolerable, but do not abolish the symptom.

To date, the preponderance of research evaluating the feasibility of electrical stimulation for suppression of tinnitus comes from studies examining cochlear implantation and promontory stimulation [7]. Cochlear implantation is currently the gold standard for rehabilitation of severe to profound sensorineural hearing loss and a demonstrated byproduct of cochlear implant electrical stimulation is tinnitus suppression. A recent review of the literature evaluating the efficacy of cochlear implantation for treatment of tinnitus in patients with single-sided deafness reveals that tinnitus is improved in 82% to 100% of implantees, abolished in 14% to 100% of implantees and none of the studies reported worsening of tinnitus during device use [10]. Despite these promising findings, cochlear implantation cannot be feasibly applied to patients with normal to moderate hearing loss, which comprises the majority of the population with tinnitus, since placement of an *intracochlear* electrode commonly results in significant hearing loss or deafness.

Promontory stimulation is an established otologic procedure that was initially developed as a diagnostic tool to assess patient candidacy for cochlear implantation. Promontory stimulation is most commonly performed in the outpatient setting on an awake patient by placing a single insulated probe through a topically anesthetized tympanic membrane and applying monopolar current for several seconds to minutes. The safety and efficacy of *transtympanic* promontory stimulation for the temporary relief of tinnitus in patients with normal hearing and varying degrees of hearing loss has recently been evaluated [3]. Overall, the literature supports that 45% to 86% of subjects gain significant or complete suppression of tinnitus according to different measures and varying stimulation parameters. Furthermore, in most cases, electrical stimulation can be successfully administered with either no perception or only transient and minimal perception [4]. When evaluating the efficacy of tinnitus suppression according to underlying etiology, it has been found that patients with acoustic trauma or noise-induced hearing loss had the highest success rates of tinnitus suppression compared to other etiologies such as presbycusis or Ménière's disease [5]. However, most patients only experience tinnitus suppression during and shortly after active electrical stimulation, with a smaller subset enjoying

residual inhibition for hours to days after treatment [5-6]. Thus, while successful at providing temporary reprieve, the method of *transstympatic* promontory stimulation utilizing an external system does not provide a solution to manage chronic tinnitus. To suppress tinnitus long-term, patients must have access to continuous or repetitive electrical stimulation.

From these data, the investigators hypothesize that a partially- or totally-implantable device, capable of administering electrical stimulation via cochlear surface (i.e., promontory), will provide safe and effective long-term suppression of tinnitus in patients with normal to moderate sensorineural hearing loss. Paramount to the development of an implantable device, the optimum region(s) of device placement in relation to the cochlear turns (i.e., basal, mid, apical or multiple levels) must be evaluated. Placement of the electrode in the region of the posteroinferior promontory or at the round window can effectively stimulate the basal turn of the cochlea, which corresponds to high-frequency regions of the tonotopic map. In contrast, placement in the region of the anterosuperior cochlear surface, inferior to the cochleaform process for example, can stimulate the mid- and apical turns of the cochlea, which correspond to mid- and low-frequency regions of the cochlear tonotopic map. Several studies have demonstrated successful electrical suppression of tinnitus through promontory stimulation in the region of the round window, while other studies have suggested that the region of optimal stimulation varies across subjects and more complete “cochlear coverage” is beneficial [11].

### 3 STUDY OBJECTIVES

**Primary Objective:** To characterize the safety and efficacy of cochlear promontory stimulation in the short-term relief of tinnitus.

**Hypothesis:** Cochlear promontory stimulation is a safe procedure that provides short term tinnitus relief to a select subset of patients with chronic tinnitus.

**Secondary Objective:** To determine the optimum region(s) of the cochlear promontory in planning for an implantable electrical device for long term tinnitus suppression.

**Hypothesis:** Electrical suppression of tinnitus is dependent on the cochlear tonotopic map, with an optimum region for tinnitus suppression individualized to each patient.

### 4 STUDY DESIGN

#### 4.1 General Design

1. Experimental approach: adult patients with normal to moderate hearing loss and disruptive intractable asymmetric tonal tinnitus will be recruited for electrical promontory stimulation testing.
2. Candidate subjects will undergo a temporal bone Computed Tomography (CT) scan, contrast enhanced head Magnetic Resonance Imaging (MRI), audiogram with immittance testing, pitch and level matching of tinnitus, Distortion Product Otoacoustic Emissions (DPOAE) and Auditory Brainstem Response (ABR) testing prior to promontory stimulation. Head MRI, DPOAE, audiogram and immittance testing are considered clinically routine for assessment of asymmetric tinnitus. Temporal bone CT, ABR, tinnitus pitch, level matching, masking levels and residual inhibition testing are not standard clinical assessments for asymmetric tinnitus. In addition, subjects will complete the Tinnitus Handicap Inventory (THI), Tinnitus Functional Index (TFI) and Tinnitus Visual Analog Scale (VAS)-L (loudness) and Tinnitus VAS-A (annoyance) questionnaires three separate times within the 10 days prior to promontory stimulation testing. Additional testing for comorbid anxiety and depressive conditions will be a screening Generalized Anxiety Disorder (GAD7), Patient Health Questionnaire (PHQ8), and short Health Anxiety Inventory (HAI-S). The NEO Personality Inventory (NEO PI) will be administered to provide baseline information. The initial session of promontory stimulation will define safety stimulation parameters, with a continual treatment after defining these parameters. After treatment is completed, the patient will complete the THI, TFI, and Tinnitus VAS-A and Tinnitus VAS-L immediately prior to stimulation, during stimulation, and following completion of stimulation at 10-minutes, 1-hour, 24-hours, 48-hours, and 1-week (or prior to the next scheduled stimulation treatment, whichever occurs first) following completion of stimulation. There will also be a “recall survey” in which patients will recall the time and feeling that their tinnitus felt in the week after the stimulation procedure. In addition, pitch and level matching of tinnitus will be completed prior to the first promontory stimulation session and after the last session. Each patient

will undergo three successive treatments separated by 7 days (+14/- 2 days). Prior to each treatment, the patient will receive an audiogram and DPOAE testing to document interval safety. At the conclusion of the study, subjects will be asked about their willingness to undergo surgical implantation of a device capable of long-term scheduled or on-demand electrical stimulation for tinnitus suppression.

#### **4.2 Primary Study Endpoints**

The primary study endpoints include tinnitus relief based upon questionnaires and tinnitus matching, tactile and auditory feedback, and the perception of discomfort during stimulation.

#### **4.3 Secondary Study Endpoints**

The secondary study endpoints include determining treatment parameters of the cochlear promontory for maximum tinnitus suppression.

#### **4.4 Early termination**

If during the pilot study the placement or use of the cochlear promontory stimulation electrode is documented or suspected by the surgeon to cause sensorineural hearing loss or undue discomfort, the study protocol will be revisited and re-written or the study will be terminated.

#### **4.5 Risk / Benefits**

**Benefit:** We propose a study evaluating short term suppression of tinnitus with the information accumulated to aid in the development of a future implantable device capable of providing long term tinnitus suppression.

**Risk:** There is a 1.6% risk of persistent tympanic membrane perforation; the risk of perforation requiring intervention is 0.5% [13]. The risk of electrical current spread on the surface of the promontory could theoretically cause facial nerve stimulation, discomfort through stimulation of the tympanic plexus, or hearing loss. CT scans involve exposure to radiation. The amount of radiation from these studies has a low risk of harmful effects.

## 5 SUBJECT ENROLLMENT AND WITHDRAWAL

### 5.1 Inclusion Criteria

- Age: 18 years of age or older
- Normal to moderate sensorineural hearing loss (based on PTA of 500, 1000 and 2000 Hz) and a word recognition score equal to or greater than 60%
- Asymmetric or unilateral subjective tonal tinnitus
- Tinnitus that is disruptive by at least two of the three criteria:
  - Determined by THI score (in the severe range i.e.  $\geq 56/100$ )
  - TFI (in the severe range i.e.  $\geq 52/100$ )
  - Tinnitus VAS ( $\geq 5/10$ )
- Tinnitus that is intractable, and has not been ameliorated by conventional measures such as a hearing aid or masking, when such interventions are potentially clinically indicated (e.g., it is not expected that people with minimal or no hearing loss would trial a conventional hearing aid)
- MRI of the head that does not reveal any anatomical or structural abnormalities of the inner ear, cochlear nerve, or brainstem that would negatively impact response to study intervention (e.g., vestibular schwannoma)

### 5.2 Exclusion Criteria

- Age: less than 18 years of age
- Subjectively severe tinnitus present less than 6 months or longer than 12 years; it is permissible to include people who have had intermittent or constant tinnitus longer than 12 years as long as it was not perceived as severe longer than 12 years
- History of brain or major ear surgery
- Prior major head trauma, defined for the purposes of this study as head trauma that results in sudden injury that causes damage to the brain and results in lasting cognitive impairment
- Ongoing clinical diagnosis of depression or anxiety; for the purposes of this study, it is permissible to include people who: 1. have a past history of clinically diagnosed depression or anxiety that is no longer currently active; or 2. people who have depressive or anxious symptoms that are thought to primarily result from severe tinnitus
  - Determined by screening using the GAD 7, PHQ8, and HAI-S
    - GAD7  $> 9$  (indicates clinically significant anxiety)
    - PHQ  $> 9$  (indicates clinically significant depression)
    - HAI-S  $> 25$  (hypochondriacal level illness anxiety)
- Inability to assess, continue or complete trial
- Currently on regularly scheduled antidepressants, anxiolytics, or antipsychotics; for this study, it is permissible to include people who use such medications at lower doses as a sleep aid or for people who intermittently use such medications for situational anxiety (e.g., Ativan before airplane travel)
- Active use of other tinnitus treatments; for the purposes of this study it is permissible to include people who prefer to use a hearing aid to amplify ipsilateral hearing loss
- Known pregnancy

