#### **5.4 Withdrawal of Subjects**

Patients who are not able to be evaluated on the date of appointment or those who should choose to withdraw for any reason will have the option to withdraw at any time.

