### 6.2 First Clinical Visit

1. Patients enrolled in the study will proceed to Mayo Clinic Otorhinolaryngology Department for additional evaluation. Candidate subjects will undergo a temporal bone CT, contrast enhanced head MRI, audiogram with immittance testing, pitch and level matching of tinnitus, and DPOAE and ABR testing prior to promontory stimulation. If during the course of the patient's visit, any of the exclusion criteria are met, the patient will be withdrawn from the study, and will be notified of this as soon as possible. If the patient has already had a temporal bone CT and/or a head MRI, they do not need to get another for this study.
  - a. The number and estimated length of each study visit

- i. 5 visits in total. The first visit would include a ~30 minute overview. The next visit would require ~2 min temporal bone CT, ~45 min MRI with contrast, ~45 min ABR, ~45 min audiogram and DPOAE, ~30-60 min of stimulation. The next 2 visits would require ~30-60 min stimulation. The last visit would require ~20 min for tympanic membrane evaluation for residual perforation and ~45 min for audiogram.

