## 7.2 Data Analysis

### a Power Analysis

Assuming the power was 80% and a **one** sided alpha of .05; we sought to determine a power analysis to detect a clinically significant decrease in tinnitus symptoms [3,12].

True Change in THI	SD of Change of THI	Sample Size		
		Equality	Superiority using 7 as bottom threshold	Superiority using 5 as bottom threshold
7	10	11		156
7	15	22		350
7	20	38		619
10	10	6	71	27
10	15	12	156	58
10	20	19	277	101
15	10	4	12	8
15	15	4	24	16
15	20	6	41	27

There are three different types of analysis used above to calculate sample size.

The first analysis shown is an equality test which assesses whether the mean change in THI level is different from zero. This is the simplest power calculation and is usually associated with a t-test. In our research question, we would like to consider the procedure a success if the scores improve significantly by a certain amount. This test only examines that, if the true change is 7 (10), it is different from zero.

The second two analyses seek to quantify the amount of change in THI we would like to consider clinically relevant. If we believe a clinically relevant change is 7 points on the THI scale we want to ensure that we have sufficient sample size to detect a mean change at or higher than 7. The final sample size column is less stringent in the mean we have to detect to consider the treatment a success, with requiring only a 5 point change to be clinically relevant (the threshold for not improving in the paper above).

The power calculation suggests that if we believe our true mean change to be a 15 THI points with a SD of 15, a difference greater than or equal to 5 can be detected using 16 subjects, while if we want to **detect a mean change greater than 7 we would need 24 subjects.**

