#### b Data Analysis

THI, TFI and Tinnitus VAS scores will be analyzed based on numeric change over time after each promontory stimulation procedure. Data from the Audiograms / DPOAE will be assessed to ensure no baseline change in hearing has occurred as safety precautionary measures.

The NEO PI will be evaluated to determine correlation between tinnitus improvement scores and baseline personality assessment. Results of the NEO PI will not be used to screen for enrollment.

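### Sections 5.2 and 6.2, read literally, allow a subject who cannot tolerate stimulation to be withdrawn as ineligible, and nothing keeps that subject in follow-up or analysis

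*Combined protocol and SAP*

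**What the plan says.** - **Eligibility.** Section 5.2 includes "Inability to assess, continue or complete trial" among the exclusion criteria. It does not limit this to inability expected at screening.
- **Withdrawal rule.** Section 6.2 (First Clinical Visit) states that if, during the visit, "any of the exclusion criteria are met, the patient will be withdrawn from the study".
- **What that visit contains.** In the visit schedule in 6.2, the imaging and hearing work-up shares a visit with stimulation: "45 min audiogram and DPOAE, ~30-60 min of stimulation". Section 6.2.1 also places stimulation at the first clinical appointment.
- **Endpoints.** Besides tinnitus relief, the primary endpoints in 4.2 include "tactile and auditory feedback, and the perception of discomfort during stimulation".
- **Other withdrawal text.** Section 5.4 covers patients who cannot be evaluated on the appointment date, and "those who should choose to withdraw for any reason will have the option to withdraw at any time". It does not mention recording reasons, continued follow-up or use of data already collected.
- **Study-level safeguard.** Under 4.4, if the electrode is documented or suspected to cause "sensorineural hearing loss or undue discomfort, the study protocol will be revisited and re-written or the study will be terminated".
- **Analysis.** Section 7.2b says "THI, TFI and Tinnitus VAS scores will be analyzed based on numeric change over time after each promontory stimulation procedure". It names no analysis population and no rule for missing scores.

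**The concern.** To continue or to complete is something a subject does after starting. When such an item is an exclusion criterion, and meeting any exclusion criterion at a stimulation visit requires withdrawal, intolerance of the procedure becomes both a primary outcome and a ground for ineligibility.

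The study has one group and analyses change from before stimulation, so no comparator arm offsets selective loss. If those who leave benefit less than those who stay, the mean THI improvement among those who stay is too large. If those who leave do so because of discomfort, and are then treated as never eligible, the discomfort result is too favourable. Safety is exposed as well: a subject withdrawn at the first session has no stated route to the later hearing tests or to the tympanic membrane check. The primary objective is to characterize both safety and efficacy, so both halves of it are affected.

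**Working it through.** **1. Can the rule reach a stimulated subject?** The sentence in 6.2 follows the list of tests done before stimulation and precedes the allowance for reusing an earlier CT or MRI, so its setting is the work-up. But its scope is the patient's visit, that visit includes the first stimulation, and no words end the rule before the needle goes in. A literal reading therefore reaches a subject who stops at session one. The rule is not repeated for sessions two and three.

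**2. Does anything keep that subject in the study?**
- Questionnaires (6.2.1, 7.1): due from 10 minutes to 1 week after stimulation, with no provision for a withdrawn subject.
- Audiogram and DPOAE (4.1, 6.2.1): done before each treatment, so someone with no further treatment has no further test at those points. The final audiogram belongs to the last visit in 6.2.
- Tympanic membrane check (6.3): timed from the end of all three stimulation visits. Section 4.5 gives a 1.6% risk of persistent perforation.
- Analysis (7.2b): no population is defined. Subjects without post-stimulation scores drop out of a change score by default.

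**3. The plan's own figure.** Section 7.2a starts from "Assuming the power was 80% and a one sided alpha of .05" and states 24 subjects to show a mean THI change above 7 when the true change is 15 and the SD is 15. A one-sided one-sample t-test (noncentral t, difference 15 − 7 = 8) gives n = 24, an exact match. The normal approximation, (15 × (1.645 + 0.842) / 8)² = 21.7, gives 22.

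**4. Illustration of a completers-only analysis.** From the documents: one-sided alpha 0.05, SD 15, threshold 7 (all 7.2a) and target accrual 100 (Study Summary). Assumed: a fraction q stops, stoppers have zero change, the true mean over all stimulated subjects is exactly 7, completers have SD 15, and completers alone are tested against 7.

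Completer mean = 7 / (1 − q), and n = 100 × (1 − q). The chance of declaring a change above 7 is approximately Φ((completer mean − 7) × √n / 15 − 1.645).

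| q | n | Completer mean | Shift in SE units | Chance (normal) | Chance (noncentral t) |
|---|---|---|---|---|---|
| 5% | 95 | 7.37 | 0.239 | 0.080 | 0.080 |
| 10% | 90 | 7.78 | 0.492 | 0.124 | 0.124 |
| 20% | 80 | 8.75 | 1.043 | 0.274 | 0.271 |
| 30% | 70 | 10.00 | 1.673 | 0.511 | 0.505 |

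With 24 stimulated and 20% stopping, 19 completers remain. The shift is 1.75 × √19 / 15 = 0.509, and the chance is 0.124 (noncentral t) or 0.128 (normal).

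**5. Direction for discomfort.** If a share w of subjects with discomfort were withdrawn and not counted, a true rate p would be seen as p(1 − w) / (1 − pw). For an assumed p of 20%, w = 25% gives 0.15 / 0.95 = 15.8%, and w = 50% gives 0.10 / 0.90 = 11.1%. Neither p nor w is in the documents. If every stimulated subject is counted, this bias is absent.

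**The case against.** The best reply is that this is a screening rule. The criterion sits among characteristics such as age, prior surgery, medication and pregnancy. Inability to attend or to complete repeated questionnaires can be judged in advance. The 6.2 sentence also promises to notify the patient as soon as possible, which suits a scan result better than intolerance the patient has just reported. This probably describes the intent, but the text does not say so, and stating it costs a few words.

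A reader might infer that the plan discards the data of withdrawn subjects or prescribes a completers-only analysis. It does neither. Section 6.2 speaks of withdrawal from the study, and 7.2b analyses change after each procedure without requiring all three. The possible bias comes from a mandatory withdrawal rule combined with silence about what follows.

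A reader might also infer that intolerable discomfort could vanish from the results. That would need every such case to be withdrawn and left uncounted, and to be missed under 4.4. The documents do not support it: discomfort level is assessed during calibration (6.2.1), and 4.4 requires study-level action on undue discomfort.

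The numbers are fairly called hypothetical. No stopping rate is given. Section 6.2.1 sets the upper limit at a level that is loud but not uncomfortable, and the Background reports little or no perception of stimulation in most cases, so stopping may be rare. The threshold of 7 comes from the power section, and 7.2b specifies no test against it. These points limit the size of the problem and leave the gap itself open.

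**Conclusion.** The concern holds as a risk that the wording permits; the documents do not set out a procedure that removes data. Sections 5.2 and 6.2 together give a route by which a subject who cannot tolerate the first session is withdrawn as ineligible, and 5.4, 6.3 and 7.2b do not hold that subject in follow-up or analysis. The THI change could be overstated, and discomfort and safety events under-counted.

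The size is unknown. On the assumptions in step 4 of the working, the error rate with 100 stimulated runs from about 8% at 5% stopping to about 51% at 30%, and is about 12% at 20% stopping with 24 stimulated. If stoppers benefit as much as completers, or if everyone stimulated is followed and analysed, the efficacy bias disappears. If they are analysed but their later scores are missing, it depends on how those scores are handled. The plan should be amended because the route is written into a mandatory rule and is cheap to close.

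**What to change.** - **5.2:** limit the criterion to a judgement made before the first needle insertion.
- **6.2:** limit withdrawal for ineligibility to the work-up before stimulation. State that a subject who later stops stimulation stays in follow-up unless consent is withdrawn, and that the reason for stopping is recorded.
- **7.2b:** analyse safety and discomfort in everyone with at least one needle insertion, and efficacy in everyone who received any stimulation.
- **Follow-up:** keep the planned questionnaires, audiogram/DPOAE and tympanic membrane check for those who stop.

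The decision on when stimulation stops remains with the investigators.

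Cost: a short amendment and follow-up that is already planned, for what are likely to be few subjects. The reported mean change may be slightly less favourable.
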